Study

This study is a single center, randomized, controlled, and double-blinded trial. The protocol of this study was approved by the Institutional Review Board of Seoul National University Bundang Hospital (No B-1701-1378-006) and registered at www.clinicaltrials.gov (NCT#03039543). Informed consents were obtained from all patients before the conduction of the study.

Patients

Patients aged more than 19 years who are American Society of Anesthesiologists (ASA) physical status I and II and scheduled to undergo elective TURB were included for this trial. Exclusion criteria are a history of neuromuscular, renal, or hepatic disease, a body mass index (BMI) of < 18.5 or > 30.0 kg/m², and treatment with drugs known to interfere with neuromuscular function.

Randomization and intervention

Randomization is conducted by a person who was not involved in the study using a computer - generated randomization code (Random Allocation Software, version 2.0). The result of randomization was sealed in an opaque envelope, which was delivered to the anesthesiologist who is in charge of the patient. Patients, surgeons and outcome assessors for recovery profiles were blinded to the group assignment. However, the anesthesiologist responsible for the patients during surgery was not blinded to the assigned group. From a table of random numbers, a total of 108 patients undergoing elective TURB are randomized into either moderate NMB group (n = 54) or deep NMB group (n = 54).

Moderate NMB group: During maintenance of anesthesia, added bolus doses of intravenous rocuronium (5–10 mg) were used to maintain moderate NMB (TOF count of 1 or 2) if needed. After the surgery, patients were reversed with 2 mg/kg sugammadex at a TOF count of 1 or 2. Deep NMB group: During maintenance of anesthesia, added bolus doses of intravenous rocuronium (5–10 mg) were used to maintain deep NMB (TOF count of 0 with PTC of 2) if needed. After the surgery, patients were reversed with 4 mg/kg sugammadex at PTC of 2.

Anesthesia

Premedication was administered with intravenous midazolam (0.02 mg/kg) as a premedication at the reception area of operating theater and then transferred to the operating room. In the operating room, standard monitoring, including electrocardiography, noninvasive arterial pressure measurements, and pulse oximetry was placed. The level of NMB was monitored using acceleromyography (TOF-Watch® SX, Organon Ireland Ltd., a subsidiary of Merck & Co., Inc., Swords, Co. Dublin, Ireland) at the adductor pollicis muscle. The TOF ratio was recorded for each patient every 5 min during the operation. The TOFwatch was calibrated in each patient before performing the measurements. The stimulation current was set to 30 mA and the TOF-watch SX was calibrated in the calibration 1 mode. During induction of anesthesia, patients received propofol (2 mg/kg) and alfentanil and the Igel[™] (Intersurgical Ltd, Wokingham, UK) was inserted after the administration of 0.6 mg/kg rocuronium in both groups. Anesthesia was maintained with desflurane while monitoring the bispectral index (A-2000 BISTM monitor; Aspect Medical Systems, Inc., Natick, MA, USA) between 40-60. A bolus dose of intravenous rocuronium (5-10 mg) was used to maintain moderate (moderate NMB group, TOF count of 1 or 2) or deep (deep NMB group, TOF count of 0 with PTC of 2) NMB if needed. At the end of the operation, the surgeon rated the endoscopic surgical condition on a 5-point scale (1 = extremely poor, 2 = poor, 3 =

acceptable, 4 = good, 5= optimal, Table 1) [9]. Patients in moderate NMB group are reversed with 2 mg/kg sugammadex at a TOF count of 1 or 2 (group A) and patients in the deep NMB group are reversed with 4 mg/kg sugammadex at PTC of 2 (group B). Patients were extubated when spontaneous ventilation of the patient was adequate. After the surgery, patients were transferred to the post-anesthesia care unit (PACU)

Postoperative residual curarization (PORC, TOF ratio < 0.9) is recorded if it occurred. Patients were evaluated every 15 min using the modified Aldrete scoring system until ready for discharge from the PACU and the criterion used for patient discharge was the achievement of a modified Aldrete score of 9 [10]. Respiratory complication such as desaturation (SpO2 < 90%) or respiratory depression (RR < 8) and other adverse events including postoperative nausea and/or vomiting (PONV) were recorded during PACU stay.

Outcome measurement

Primary outcome was the endoscopic surgical condition that was evaluated right after the operation by the surgeon (Table 1), who was blinded to the group assignment. Secondary outcomes were recovery profiles including the postoperative residual curarization (PORC, TOF ratio < 0.9), respiratory complications, recovery time (PACU discharge, a modified Aldrete score of 9) and other postoperative adverse events.

Sample size

The sample size was calculated based on the preliminary data using G*Power 3.1.2 (Heinrich-Heine University, Düsseldorf, Germany). The proportion of optimal endoscopic surgical condition (score 5) during TURB was 30 % after the use of moderate NMB (n = 10) and 30% increase of optimal endoscopic surgical condition by deep NMB was considered to

be clinically significant. Fifty four (54) patients per group was calculated with $\alpha = 0.05$ and $\beta = 0.2$, allowing for a 10 % drop-out rate.

Statistical analysis

Statistical analysis is performed using SPSS 21 (SPSS Inc., Chicago, IL, USA) and the test of normal distribution was assessed with the Shapiro–Wilk test. Chi-square test or Fisher's exact test was used for the analysis of incidence variables (gender, ASA physical class, additional rocuronium, surgical condition score, PORC, respiratory complications and other adverse events). Student's t test is used to compare normally distributed continuous variables (age, weight, height, BMI, operation time, anesthesia time, propofol, alfentanil, rocuronium, and recovery time). All values presented are number of patients (%) or mean (SD). A p values < 0.05 were considered to indicate statistical significance.

Score	Surgical condition	
1.	Extremely poor conditions	The surgeon is unable to work because of coughing or
		because of the inability to obtain a endoscopic view
		because of inadequate muscle relaxation. Additional
		neuromuscular blocking agents must be given
2.	Poor conditions	There is a endoscopic view but the surgeon is severely
		hampered by inadequate muscle relaxation with
		continuous muscle contractions, movements, or both
		with the hazard of tissue damage. Additional
		neuromuscular blocking agents must be given
3.	Acceptable conditions	There is a wide endoscopic view but bladder
		contractions, movements, or both occur regularly
		causing some interference with the surgeon's work.
		There is the need for additional neuromuscular
		blocking agents to prevent deterioration
4.	Good conditions	There is a wide endoscopic working field with
		sporadic muscle contractions, movements, or both.
		There is no immediate need for additional
		neuromuscular blocking agents unless there is the fear
		of deterioration
5.	Optimal conditions	There is a wide endoscopic working field without any
		movement or contractions. There is no need for
		additional neuromuscular blocking agents

Table 1. Surgical condition score (Ref 7 by Martini et al.)

Surgical conditions were evaluated right after the surgery by the surgeon, who was blinded to the group assignment.

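### Does residual curarization lack a usable definition because no post-reversal reading time is written down?

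*SAP*

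**What the plan says.** The Outcome measurement section of the SAP lists PORC, with its threshold, as a secondary outcome: "Secondary outcomes were recovery profiles including the postoperative residual curarization (PORC, TOF ratio < 0.9". The Statistical analysis section includes it among the variables covered by this rule: "Chi-square test or Fisher's exact test was used for the analysis of incidence variables".

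On collection, the Anesthesia section says "Postoperative residual curarization (PORC, TOF ratio < 0.9) is recorded if it occurred". The other relevant statements are:

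- TOF ratio in surgery (Anesthesia): "The TOF ratio was recorded for each patient every 5 min during the operation".
- Reversal, moderate arm (Randomization and intervention): "After the surgery, patients were reversed with 2 mg/kg sugammadex at a TOF count of 1 or 2".
- Reversal, deep arm (same section): "After the surgery, patients were reversed with 4 mg/kg sugammadex at PTC of 2".
- PACU follow-up (Anesthesia): "Patients were evaluated every 15 min using the modified Aldrete scoring system until ready for discharge from the PACU".
- Blinding (Randomization and intervention): "Patients, surgeons and outcome assessors for recovery profiles were blinded to the group assignment".

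**The concern.** PORC is a threshold on a measured quantity. Unlike vomiting or desaturation, it does not show itself unless the nerve is stimulated and the response read. A rule that records it when it happens can therefore be taken to mean that only suspected cases are measured.

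The schedules elsewhere in the SAP do not settle the matter. The five-minute TOF ratios belong to the operation, and reversal comes after it. Extubation depends on adequate spontaneous breathing, which implies no TOF reading. The PACU schedule is for the Aldrete score. Respiratory and other adverse events are tied to the PACU stay, but PORC has no window of its own.

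Two things would be at stake. First, the ratio rises after reversal, and the arms are reversed from different depths of block, so readings at unequal times could differ between arms through timing alone. Second, if some patients were not read and were counted as free of PORC, a low count could reflect missing readings and not good recovery.

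**Working it through.** **The plan's own figure.** The SAP gives no expected rate or precision for PORC. Its only planned number is 54 per group, for the primary outcome. With 30% against 60%, two-sided alpha 0.05 (the SAP does not state sidedness) and power 0.80, the exact power of Fisher's test is 0.786 at 47 per group and 0.800 at 48. Allowing for 10% drop-out, 48 / 0.9 = 53.3, rounded up to 54. The figure reproduces and does not depend on PORC.

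**Is the time really open?** The TOF ratio is the fourth twitch divided by the first. At a TOF count of 0, 1 or 2 there is no fourth twitch, so no patient reversed as planned could reach 0.9 at that moment. Read then, PORC would be 54/54 in both arms. The SAP does not support that reading, for three reasons:

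1. The outcome is named as postoperative and residual, so it is what remains after reversal.
2. In the Anesthesia section its sentence follows reversal, extubation and transfer to the PACU, and comes directly before the 15-minute PACU evaluations.
3. Outcome measurement places it among the recovery profiles, whose assessors are blinded under Randomization and intervention.

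What is unstated is the exact time within early recovery.

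**Is the denominator open?** The number randomized is 54 per arm, and the Statistical analysis section presents results as number of patients with percentage. The number actually read is not stated, but for any outcome that is known only once the data are in.

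**What missing readings would do.** For 0 events in n patients, the exact two-sided 95% upper limit is 1 − 0.025^(1/n). Only n = 54 comes from the document; the other values are assumptions.

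| Patients read in an arm | Upper limit for a zero count |
|---|---|
| 54 | 6.6% |
| 40 (assumed) | 8.8% |
| 27 (assumed) | 12.8% |
| 10 (assumed) | 30.8% |

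**What unequal reading would do.** Suppose a true rate of 10% in both arms, all 54 read in one arm and half in the other, and unread patients counted as having no PORC. The expected counts are 54 × 0.10 = 5.4 and 54 × 0.5 × 0.10 = 2.7. The apparent rates are 5.4/54 = 10% and 2.7/54 = 5%, with no true difference. Dividing the second count by the 27 patients read gives 2.7/27 = 10%, so the gap disappears if missingness is unrelated to PORC. The gap needs unequal reading and an unsuitable denominator, and the SAP prescribes neither.

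**The case for a change.** The strongest case for a change is that this document does not leave measurement to the protocol. It gives the device, muscle, current, calibration mode, the five-minute TOF schedule and the 15-minute Aldrete schedule. Against that background, PORC has a rule by exception, which could be called an outcome badly fixed and not merely a detail left out. A reading never taken cannot be recovered later. The anesthesiologist in theatre is unblinded, and the SAP does not say outright who takes the PORC reading.

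Part of this stands. No sentence gives a common time after reversal or says that every patient is read, and a late or absent reading would be lost for good.

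The rest is weaker. Setting out some procedures does not oblige a SAP to set out all of them. The collection rule can be read as a plain yes/no entry for a binary event; it does not say that a reading is taken only on suspicion. Reversal in both arms is timed by TOF count or post-tetanic count after surgery, so monitoring already runs past the operation in every patient. That does not prove a later reading, but it makes widespread non-measurement less plausible. On who reads, the listing under recovery profiles points to the blinded assessors.

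**Conclusion.** No change to the plan follows. This is missing detail of a kind that investigators and analysts fill sensibly: a post-reversal reading in recovery, PORC reported among patients with a reading, and the number without one shown by arm. The SAP states nothing wrong and contradicts nothing on this point, and no rule in it has been shown to give a wrong result.

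If every patient is read, a zero count in an arm of 54 excludes rates above 6.6%. The larger limits and the 10% against 5% contrast describe what missing readings would do in any trial and rest on assumed figures.

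The conclusion assumes that the reading is taken after reversal, as the order of the text and the name of the outcome indicate, and that the protocol or case report form carries the timing. If TOF ratios were in fact read only on suspicion, the comparison of PORC between arms would deserve little weight. Even then the damage would be confined to one of several secondary outcomes, with the primary outcome and the 54 per group unaffected.

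### Does the plan need to say which part of the operation the surgeon's single rating covers, and does Table 1's dosing wording conflict with the bolus rules?

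*SAP*

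**What the plan says.** The SAP describes the rating in three places, and they agree.

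- Anesthesia: "At the end of the operation, the surgeon rated the endoscopic surgical condition on a 5-point scale".
- Outcome measurement: the primary outcome is the "endoscopic surgical condition that was evaluated right after the operation by the surgeon (Table 1").
- Note under Table 1: "Surgical conditions were evaluated right after the surgery by the surgeon, who was blinded to the group assignment".

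There is therefore one score per patient, given by a blinded surgeon once the operation is over. None of the three places names the period being rated.

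In Table 1 the anchor for score 5 begins "There is a wide endoscopic working field without any" and goes on to exclude all movement and contraction. Score 4 tolerates sporadic ones. The Sample size section is built on score 5: "The proportion of optimal endoscopic surgical condition (score 5) during TURB was 30" per cent in ten patients under moderate block. A 30% increase counts as clinically significant, and this leads to 54 per group.

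On dosing, the anchors for scores 1 and 2 end by saying that additional "neuromuscular blocking agents must be given", and score 3 mentions a need for them. The Randomization and intervention section ties boluses to the assigned depth. In the moderate arm they are "used to maintain moderate NMB (TOF count of 1 or 2) if needed", with a matching statement for the deep arm. The Anesthesia section repeats the rule.

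**The concern.** The gap falls on the boundary between scores 4 and 5, the boundary used to size the trial. A patient with one early contraction and a still field at the end is at most a 4 if the whole operation is rated, but a 5 if only the final state is. Two surgeons could follow the text and score the same operation differently. If a final-state reading lifted patients to 5 in both arms, the difference between arms would shrink.

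The dosing wording adds a second worry. Taken as an instruction, Table 1 could call for extra blocker in a moderate-arm patient who is already at the target depth. That patient might then be rated 5 on the later state, which would pull the arms together. The trial compares depths of block, so this would act directly on the primary contrast.

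**Working it through.** **1. The plan's own figure.** Inputs from Sample size: 30% under moderate block, a 30% increase read as absolute (so 60%), alpha 0.05 (taken as two-sided), power 80%, drop-out 10%. The exact power of Fisher's test is 78.6% at 47 per arm and 80.0% at 48. Then 48 / 0.9 = 53.3, rounded up to 54. The stated size reproduces, and the concern disputes no figure in it.

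**2. Which period does the text imply?**

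- Table 1 separates the scores by frequency: continuous at 2, regular at 3, sporadic at 4, none at 5. Frequencies need a stretch of time to be observed.
- Score 1 describes a surgeon who cannot work. That can hardly be the closing state of an operation just completed, so a final-state reading would nearly empty the low end of the scale.
- The Sample size section counts score 5 over the procedure ("The proportion of optimal endoscopic surgical condition (score 5) during TURB was 30" per cent).
- A single score given after the operation is most naturally a retrospective summary.
- Against this, the anchors are in the present tense, and score 4 speaks of no immediate need for more blocker.

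The balance is clearly towards the whole operation.

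**3. Is there a conflict over dosing?** The bolus rule appears twice and both times is tied to the monitored depth. The scale is attributed to a published source and scored after surgery, so a score cannot prompt a dose during the operation. The two texts would diverge only if Table 1 were meant as an instruction and conditions were poor while the moderate target was held. Nothing says it was so meant.

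**4. What would it take to matter?** The figures below are exact power of Fisher's test for score 5 against below 5, with 48 per arm, two-sided 0.05. Every shift is assumed.

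(a) Doses driven by conditions, moderate arm only. Moderate rate = 0.30 + (share affected) × (chance of then being rated 5), against 0.60.

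| Share × chance | Moderate rate | Power |
|---|---|---|
| none | 0.300 | 80.0% |
| 0.05 × 0.30 | 0.315 | 75.4% |
| 0.10 × 0.30 | 0.330 | 70.2% |
| 0.10 × 0.60 | 0.360 | 58.8% |

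(b) A final-state rating lifts a share *s* of below-5 patients to 5 in both arms. Rates are 0.30 + 0.70*s* and 0.60 + 0.40*s*, so the difference is 0.30(1 − *s*).

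| *s* | Rates | Difference | Power |
|---|---|---|---|
| 0.05 | 0.335 v 0.62 | 0.285 | 75.3% |
| 0.10 | 0.37 v 0.64 | 0.27 | 70.1% |
| 0.20 | 0.44 v 0.68 | 0.24 | 58.9% |

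Scenario (a) needs doses beyond the moderate target, which the plan does not provide for, and a rating of the later state only. It costs nothing if the preliminary 30% already reflects such doses. Scenario (b) needs the preliminary data and the trial to have used different periods. If both used the same one, the 30% is already on the trial's scale and the planned 30-point difference applies to it directly. The document gives no frequencies for scores 1 to 4, so neither share can be estimated. Both scenarios also split the scale at 5, whereas Statistical analysis lists the surgical condition score for a chi-square or Fisher test without naming a cut.

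**The case for a change.** The best case for a change is this. The SAP does not leave the endpoint to another document: it defines it and prints the whole scale, so an incomplete definition is the SAP's own. The missing piece sits on the 4/5 boundary that drives the sample size. Reading the period from a phrase in the sample-size text is inference, and ten preliminary patients do not show that the same period was used before and during the trial. Blinding stops the surgeon favouring an arm, but it does not stop an equal upward shift from narrowing the difference, as scenario (b) shows. A sentence of clarification would be cheap.

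Some of this stands. The period is not written down, and blinding does not by itself rule out attenuation. What does not follow is that the plan goes wrong as written. The more natural reading is also the sound one, and a surgeon who follows it gives a valid comparison. With blinded raters and random allocation, a surgeon's habit in reading the scale falls on both arms alike, so it cannot create a difference where there is none. The loss of power needs a mismatch that nothing in the document suggests.

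The dosing argument is weaker still. Recording a reason for each bolus would add a data item but change no planned result, and the plan already compares additional rocuronium and rocuronium dose by arm.

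**Conclusion.** No change to the plan is called for. The rating period is a detail left unwritten, which a reader fills sensibly from Table 1 and the Sample size section: the score covers the whole operation. The trial report can state the period the surgeons used. Table 1's dosing phrases are most naturally descriptions of severity. Should the sponsor have meant them as instructions, they would have to be reconciled with the bolus rules, but the text gives no sign of that.

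No size can be put on any effect. The 54 per group stands, and the fall from 80% to about 59% power is the far end of assumed scenarios, not an estimate. This conclusion rests on two assumptions: that surgeons read the scale in its more natural sense, and that the preliminary 30% was scored in the same way as the trial. The document contradicts neither.

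### The trial is sized on the proportion with score 5, but the SAP never says that this proportion is what the primary test compares

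*SAP*

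**What the plan says.** The Sample size section of the SAP rests on one binary contrast. It gives the control rate as "The proportion of optimal endoscopic surgical condition (score 5) during TURB was 30 % after the use of moderate NMB (n = 10" pilot patients), and adds that a "30% increase of optimal endoscopic surgical condition by deep NMB was considered to" be clinically important. With alpha 0.05, beta 0.2 and a 10% drop-out allowance, it arrives at 54 per group.

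That contrast appears nowhere else. The Outcome measurement section states: "Primary outcome was the endoscopic surgical condition that was evaluated right after the operation by the surgeon". The Anesthesia section says that "the surgeon rated the endoscopic surgical condition on a 5-point scale", and Table 1, which describes the levels 1 to 5, is captioned as the surgical condition score.

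The Statistical analysis section assigns the chi-square test or Fisher's "exact test was used for the analysis of incidence variables (gender, ASA physical class, additional rocuronium, surgical condition score" and further items in the same list. It gives no cut-off for the score and does not single out a primary test. Its only decision rule is general: "A p values < 0.05 were considered to indicate statistical significance".

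**The concern.** The variable sent to the test carries the name that Table 1 gives to the whole five-level scale. A literal analyst would build a table of two groups by as many score levels as occur (up to five, so up to 4 degrees of freedom) and run an unordered test. An analyst guided by the Sample size section would build a 2x2 table of score 5 against below 5. The same sentence therefore supports two primary p-values.

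Three things are at stake:

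- **Power.** Only the 2x2 test on score 5 is covered by the sample size calculation.
- **Meaning.** An unordered test over all levels can reject when the score-5 rates are identical. Its p-value does not by itself show that deep block raises the rate of optimal conditions.
- **Pre-specification.** With the contrast unwritten, it can be settled after the scores have been seen, and this is the trial's only primary outcome.

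**Working it through.** **Inputs from the SAP.** Score-5 rate under moderate block 0.30; increase of 30%; alpha 0.05; power 0.80; drop-out 10%; 54 per group.

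**Assumptions.** The test is two-sided, since sidedness is not stated. The increase is absolute, 0.30 to 0.60. A relative reading (0.30 to 0.39) needs at least 437 per group two-sided before drop-out, so it cannot give 54.

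**Step 1: reproduce 54 per group.** Exact power of the 2x2 Fisher test is the sum, over all pairs (i, j) with Fisher p ≤ 0.05, of Bin(i; n, 0.30) × Bin(j; n, 0.60).

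| n per arm | Power |
|---|---|
| 47 | 78.6% |
| 48 | 80.0% |
| 54 | 83.9% |

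The smallest of these reaching 80% is 48, and 48/(1 − 0.10) = 53.3, rounded up to 54. The plan's figure is reproduced. The continuity-corrected formula gives 49, and 49 × 1.1 = 53.9 also rounds up to 54. Both routes are 2x2 calculations on score 5.

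**Step 2: power if all levels are tested.** Pearson chi-square with (levels used − 1) degrees of freedom, 200,000 simulated trials per case. Score 5 is fixed at 30% against 60%; the shares of scores 1 to 4 are assumed.

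- *Proportional shrink:* each share below 5 is multiplied by 0.4/0.7.
- *Proportional odds:* the odds ratio is (0.6/0.4)/(0.3/0.7) = 3.5.

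| Moderate arm, scores 1–5 | Change in deep arm | 48 per arm | 54 per arm |
|---|---|---|---|
| .05/.10/.20/.35/.30 | proportional shrink | 66% | 72% |
| 0/.05/.25/.40/.30 | proportional shrink | 71% | 76% |
| 0/0/.20/.50/.30 | proportional shrink | 78% | 82% |
| .05/.10/.20/.35/.30 | proportional odds | 73% | 79% |
| 0/.05/.25/.40/.30 | proportional odds | 77% | 82% |
| 0/0/.30/.40/.30 | proportional odds | 83% | 88% |
| 0/0/.30/.40/.30 | to 0/0/.05/.35/.60 | 95% | 97% |
| 0/0/0/.70/.30 | scores 4 and 5 only (a 2x2 test) | 85% | 88% |

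At the planned 48 evaluable per arm, five of the eight cases fall below 80% and three lie above it.

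**Step 3: can the two readings disagree?** Take 48 per arm, scores 1 to 5: moderate 0/3/10/20/15, deep 0/2/7/13/26.

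- Score 5: 15/48 against 26/48. The difference is 11/48 = 22.9 points (Newcombe 95% CI 3.1 to 40.3). Fisher p = 0.038.
- All levels: expected counts per arm are 2.5, 8.5, 16.5 and 20.5. Chi-square = 2 × (0.5²/2.5 + 1.5²/8.5 + 3.5²/16.5 + 5.5²/20.5) = 0.20 + 0.53 + 1.48 + 2.95 = 5.17 (unrounded terms) on 3 df, p = 0.160 (exact 0.161).

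**Step 4: can the all-levels test reject with no gain at score 5?** Moderate 0/2/7/25/14, deep 0/2/18/14/14. Score 5 is 14/48 in both arms. Chi-square = 2 × (5.5²/12.5 + 5.5²/19.5) = 4.84 + 3.10 = 7.94 on 3 df, p = 0.047 (exact 0.035). The rejection comes entirely from the deep arm having more scores of 3 and fewer of 4.

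**The case against.** The best defence is that the SAP, read as a whole, points to score 5. The score is listed among incidence variables, and nearly every other item there has two categories. ASA class does too, because only classes I and II are eligible. An incidence of a score needs a cut-off, and the only one in the document is score 5, in the section just above. On this view there is an unwritten link, not a contradiction, and a clarification would do.

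Part of this stands: the score-5 reading is plausible and probably intended. But it has to be imported from another section, while the term actually listed is the name of the full scale.

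Other points also have weight:

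- The power range straddles 80%. The 66% floor assumes that all five levels occur, including 5% of the moderate arm at score 1. If only scores 4 and 5 occur, the two readings coincide.
- The simulated power is for Pearson chi-square. Sparse tables might be sent to an exact test, whose power was not computed.
- The tables in Steps 3 and 4 are constructed. Moreover, a difference in distribution is not a false positive if the outcome really is the whole scale.
- The G*Power option is not stated, so Fisher is not the only 2x2 calculation that leads to 54.

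These limit how far one can say the trial is underpowered. None removes the second primary p-value.

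**Conclusion.** The concern holds and must be fixed. The sample size is sound for a 2x2 comparison of score 5 at 30% against 60%, but the analysis text does not commit to that comparison. If all levels are tested, 80% power is not assured: about 66% to 95% at 48 per arm and 72% to 97% at 54, under the assumed distributions. The accurate description is not assured rather than underpowered, because the direction depends on scores 1 to 4, about which the SAP is silent. The more serious consequence needs no assumption about power: two defensible readings of one sentence can give opposite primary conclusions on the same data.

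**What to change.** Remove the surgical condition score from the list of incidence variables and add a separate statement along these lines:

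> The primary analysis compares the proportion of patients with a surgical condition score of 5 (versus below 5) between groups with a two-sided Fisher exact test at 0.05. The risk difference (deep minus moderate) is reported with a 95% CI. The full 1–5 score is shown by group as a supportive outcome and compared with a method that uses its order, for example the Wilcoxon rank-sum test.

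The Outcome measurement section should name the same score-5 proportion as the primary outcome. The essential element is the cut-off together with one named test. Fisher is suggested because it reproduces the stated sample size. An uncorrected 2x2 chi-square would also be adequately powered (about 85% at 48 per arm), but the choice must be fixed in advance.

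The cost is SAP wording only. No further data or patients are needed, and 54 per group remains valid.

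### As the text reads, the full 5-point primary score gets a chi-square or Fisher test that ignores the order of the scores; the analysis section should name one primary comparison and use an ordinal test for the full score

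*SAP*

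**What the plan says.** The SAP's Outcome measurement section defines the primary endpoint without a cut-point: "Primary outcome was the endoscopic surgical condition that was evaluated right after the operation by the surgeon (Table 1"). Under Anesthesia the scale is described as ordered: "the surgeon rated the endoscopic surgical condition on a 5-point scale (1 = extremely poor, 2 = poor, 3" and so on up to 5 for optimal. Table 1 sets out the five grades, from a surgeon who cannot work to a field free of movement.

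The Statistical analysis section gives the score one method, chi-square or Fisher, in a list that also holds gender and ASA class: "exact test was used for the analysis of incidence variables (gender, ASA physical class, additional rocuronium, surgical condition score, PORC". The listed item is the score itself. The section states no cut at score 5 and names no rank, trend or ordinal method.

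A cut at score 5 appears only under Sample size: "The proportion of optimal endoscopic surgical condition (score 5) during TURB was 30 % after the use of moderate NMB (n = 10"), with "30% increase of optimal endoscopic surgical condition by deep NMB was considered to" be clinically significant. That section sets α = 0.05, β = 0.2 and 54 patients per group, "allowing for a 10 % drop-out rate".

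**The concern.** The trial asks whether deep block gives better surgical conditions than moderate block, which is a directional question on an ordered scale. A chi-square or Fisher test over the score levels returns the same p-value if the five labels are shuffled. It spends up to 4 degrees of freedom on differences of any shape. Two things follow if the full score is tested as written:

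- A significant result may reflect a wider or narrower spread of scores, and so need not support a claim that deep block is better.
- A general upward shift is detected less often than a test that uses the order would detect it, and possibly less often than the 80% the trial was planned for.

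**Working it through.** **Reproducing 54 per group.** Inputs from Sample size: 30% at score 5 under moderate block, an increase of 30 percentage points to 60%, α = 0.05, power 0.80, 10% drop-out. Sidedness is not stated; two-sided is assumed.

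- Exact two-sided Fisher power, 0.30 vs 0.60: 0.786 at n = 47 and 0.8005 at n = 48. Then 48/0.9 = 53.3, rounded up to 54. This matches.
- Continuity-corrected formula: 49 per group; 49 × 1.1 = 53.9, or 54.
- Uncorrected formula: 42 per group, 47 after drop-out. This does not match.
- A relative increase (30% to 39%) would need 437–459 per group before drop-out. This does not match.

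So 54 per group is a 2×2 comparison of score 5 against the rest, with 48 evaluable per arm.

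**Power of the candidate tests at 48 per arm.** The SAP does not give the split of scores 1–4, so splits were assumed, all with 30% at score 5. Six splits were simulated with 5,000 trials each, for scores 1–5: (.03, .07, .20, .40, .30), (.05, .10, .25, .30, .30), (0, .05, .20, .45, .30), (0, 0, .20, .50, .30), (0, 0, .10, .60, .30), (0, 0, .35, .35, .30). Three more were run with 8,000 trials each for the first two patterns below: (.05, .10, .20, .35, .30), (.02, .05, .18, .45, .30), (.10, .15, .20, .25, .30). The deep arm has 60% at score 5, reached in three ways:

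- Proportional odds: OR = (0.6/0.4)/(0.3/0.7) = 3.5.
- Proportional shrinkage: each of scores 1–4 multiplied by 0.4/0.7 = 0.571.
- 4-to-5 only: 30 points move from score 4 to score 5, and lower scores do not change.

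| Pattern | Chi-square over levels | Wilcoxon-Mann-Whitney | Fisher, score 5 | Chi-square 2×2, score 5 |
|---|---|---|---|---|
| Proportional odds | 72–84% | 87–91% | 79–81% | 85–86% |
| Proportional shrinkage | 65–79% | 77–83% | about 80% | 85–86% |
| 4-to-5 only | 83–99% | 38–73% | about 80% | about 85% |

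Across the six splits, the chi-square over levels is below 80% in three under proportional odds (72.0, 73.2 and 76.8%) and in all six under proportional shrinkage.

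**Significance without direction.** Take 54 per arm with scores 3/4/5 of 5/40/9 vs 14/22/18.

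- Mean score: (15 + 160 + 45)/54 = 220/54 and (42 + 88 + 90)/54 = 220/54, which are equal.
- Expected counts per arm are 9.5, 31 and 13.5. Chi-square = 2(4.5²/9.5) + 2(9²/31) + 2(4.5²/13.5) = 4.26 + 5.23 + 3.00 = 12.49 on 2 df, p = 0.002.
- Midranks are 10, 50.5 and 95. Rank sums are 2925 and 2961 against 2943 expected; tie-corrected p = 0.90.

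A second case holds score 5 equal. Scores 2/3/4/5 are 0/50/20/30% vs 20/6/44/30%, and the probability that a patient in the second arm scores higher, counting ties as half, is 0.534. At 48 per arm the chi-square over levels rejects in essentially all simulated trials, Wilcoxon in 10.8% and Fisher on score 5 in 2.9%.

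**Type I error.** With identical distributions the chi-square over levels rejects in 4.3–4.6% of trials, so α is not inflated.

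**The case against.** The strongest reply is that the SAP meant score 5 vs 1–4 all along. The clinically significant difference is defined only on score 5, and 54 per group reproduces exactly as a Fisher test on that cut. Table 1 also gives the cut a rationale, since score 5 is the only grade free of movement. On that reading the test is 2×2 and directional, and the planned power is met. Ignoring the ranking among scores 1–4 is then a choice of endpoint. This stands, and it limits the point to tests of the full score. It does not remove the point, because neither the outcome definition nor the analysis section adopts the cut, and the listed variable is the score.

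A reader might infer that a rank test is always the more powerful choice. The table does not support that. Under proportional shrinkage Wilcoxon is weaker than the uncorrected 2×2 chi-square on score 5. Under a pure 4-to-5 shift it is weaker than every alternative, including the multi-level chi-square. The SAP gives no split of scores 1–4, so none of these patterns can be called the likely one.

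A reader might also take the 5/40/9 vs 14/22/18 example to show that neither arm is better on any criterion. It does not: score 5 goes from 9/54 (17%) to 18/54 (33%), 2×2 chi-square 4.00, p = 0.046 (Fisher p = 0.074). It shows only that the multi-level test can reject when mean scores are equal and rank sums nearly so. The case with 30% at score 5 in both arms avoids this objection, though it is contrived.

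Finally, the stated test is valid under the null, and the SAP is not at fault for citing no guideline in its support.

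**Conclusion.** The point holds for the full score and only there. Tested over its levels as the Statistical analysis section reads, the ordered primary outcome loses its order, and a significant result need not mean that either arm is better. Power at 48 evaluable per arm is about 65–84% under proportional odds or proportional shrinkage, against about 77–91% for Wilcoxon-Mann-Whitney. These figures assume two-sided α = 0.05, 30% vs 60% at score 5, and the splits of scores 1–4 listed above. With a pure 4-to-5 shift the comparison reverses.

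The documents do not support the wider claims that the fault persists under a score-5 analysis, that an ordinal test always gains power, or that the false-positive rate is raised. The fault lies in power and interpretation. It should be corrected, but it does not invalidate the design.

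**What to change.** Before unblinding, take the surgical condition score out of the chi-square/Fisher list and replace it with text such as: *The primary analysis compares the proportion of patients with score 5 between groups by a two-sided Fisher's exact test. As a supportive analysis, the full 1–5 score is compared with a two-sided Wilcoxon-Mann-Whitney test with tie correction (or the linear-by-linear association test). The distribution of scores 1–5 is shown by group.*

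This leaves one primary test, matched to the 54 per group. It also replaces the unordered chi-square wherever the full score is compared.

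The cost is a few lines of text, with no new data or patients; the tests are standard in SPSS. The downside is that the ordinal test is clearly less sensitive to a pure 4-to-5 shift. The score-5 primary analysis covers that case.
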